3 PATIENT SELECTION

3.1 Eligibility Criteria

- 3.1.1 Subject is ≥ 18 years old
- 3.1.2 Platelet count $> 50,000/\text{mm}^3$
- 3.1.3 Eastern Cooperative Oncology Group (ECOG) Performance score of 0 to 2.
- 3.1.4 Ability to provide informed consent. All subjects must sign an informed consent form indicating their understanding of the investigational nature and risks of the study before any protocol-related studies are performed.
- 3.1.5 Categories
 - 3.1.5.1 ARM 1 only
 - 3.1.5.1.1 For patients with presumed localized disease (any T, N0, M0), a multiparametric MRI (standard of care at the NIH Clinical Center) must be performed within 4 months of the ^{18}F -DCFBC injection with findings suggestive for prostate cancer and a prostate lesion at least 6mm or greater. Must have histopathologic confirmation of prostate cancer prior to ^{18}F -DCFBC imaging.
 - 3.1.5.2 ARM 2 only:
 - 3.1.5.2.1 For patients status post radiation therapy for prostate cancer, any PSA increase from post radiation therapy nadir

OR

- 3.1.5.2.2 For patients status post prostatectomy, a PSA ≥ 0.2 ng/ml
- 3.1.5.2.3 Nonspecific or no evidence for disease on standard imaging modality
- 3.1.5.3 ARM 3 only:
 - 3.1.5.3.1 Patients must have identifiable metastatic disease on at least 1 clinically indicated imaging modality. If only soft tissue metastasis, one lesion must measure at least 6mm or greater. Patients must have confirmation of prostate cancer prior to ^{18}F -DCFBC imaging.

Note: A patient who is eligible for one arm, subsequently may cross-over into a different arm.

CC Protocol Number: 14-C-0140
Abbreviated Title: DCFBC in prostate cancer
Version date: 10/27/2015
CIP #: 9622

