To date 31 patients have been scanned on Arm 2. All are assumed to have recurrent disease based on rising PSA. There have been 20 positive scans (9 in the prostate bed, 8 outside the prostate bed (nodes or bone) and 3 both in and out of the prostate bed. Biopsy is only available in 7 but clinical information is supportive (i.e. response to therapy) in 4 more. Thus, the results are still preliminary. In the range of PSA 0.2-0.5ng/ml the scan is 25% positive, 0.5-1.0 ng/ml 50% 1.0 to 2.0ng/ml 40% and >2.0ng/ml 85%. However, the first 10 patients were done without irrigation catheters and this undoubtedly explains some of the findings. The first expansion request for Arm 2 was to get more patients with bladder irrigation catheters after we recognized that bladder-urethra activity was probably hiding some lesions. We now have over 20 patients in that category. Having shown some promising results, the purpose of this expansion cohort is to better define the sensitivity of DCFBC as a function of serum PSA. This should be a useful metric for comparing DCFBC with the next agent, DCFPyl which is reputed to have higher sensitivity. Thus, the basis of our request is to obtain more accurate assessment of the sensitivity of this agent as a function of PSA in patients with biochemical recurrence.

CC Protocol Number: 14-C-0140
Abbreviated Title: DCFBC in prostate cancer
Version date: 10/27/2015
CIP #: 9622

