4.8 Biopsy

Biopsy of abnormal sites of uptake will not be required by this protocol; however if a suspicious focus of uptake is identified, this information will be communicated to the referring physician, who may choose to evaluate the site further with biopsy or clinical follow-up. In such a case any follow-up information obtained (including pathology) will be collected as clinically needed.

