4.10 Off-Study Criteria

In cases where a subject withdraws or is withdrawn from the study after administration of ^{18}F DCFBC and before surgery or biopsy is performed, a replacement subject will be enrolled.

Should a subject withdraw after administration of ^{18}F DCFBC, or should the investigators decide to withdraw the subject, all efforts will be made to complete and report the protocol-stipulated observations up to the time of withdrawal as thoroughly as possible. A final evaluation at the time of the subject's withdrawal should be made and an explanation given of why the subject is withdrawing or being withdrawn from the study. The reason and date and time of withdrawal must be recorded. If the reason for withdrawal is a clinical AE, monitoring will continue until the outcome or stabilization is established.

Patients will be taken off treatment upon completion of all study procedures. The patients will be taken off study one year after the follow-up period. During this one year time period, the patient's PSA levels and prostate cancer related medical history, biopsy results, imaging studies and will be collected.

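### Arm 2 takes any PSA rise above the post-radiation nadir as both entry rule and proof of recurrence, so its sensitivity by PSA is really a PET-positivity rate in men of unverified disease status

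*Combined protocol and SAP*

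**What the plan says.** Arm 2 has two PSA routes in section 3.1. The post-prostatectomy route has an absolute threshold: "For patients status post prostatectomy, a PSA ≥ 0.2 ng/ml". The post-radiation route (3.1.5.2.1) has none: "For patients status post radiation therapy for prostate cancer, any PSA increase from post radiation therapy nadir". Both also need this imaging result: "Nonspecific or no evidence for disease on standard imaging modality". Imaging at entry therefore does not confirm recurrence.

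The Amendment E Addendum in section 2.3 describes the 31 Arm 2 men scanned so far: "All are assumed to have recurrent disease based on rising PSA". On verification it says: "Biopsy is only available in 7 but clinical information is supportive (i.e. response to therapy) in 4 more". It gives the percentage of positive scans by PSA band and states the aim of the expansion: "the purpose of this expansion cohort is to better define the sensitivity of DCFBC as a function of serum PSA".

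The Amendment E Addendum in section 14.1 evaluates Arm 2 by comparing PSA between PET-positive and PET-negative men. It uses a two-sided 5% Wilcoxon test with 26 negative and 52 positive men.

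On confirmation, section 3.3 requires pathology of the prostate cancer diagnosis, not of the recurrence. Section 4.1 plans biopsy validation where possible, and 12 months of follow-up to look for associations with the scan. Section 4.8 adds: "Biopsy of abnormal sites of uptake will not be required by this protocol". Section 4.10 says that over the follow-up year the patient's "PSA levels and prostate cancer related medical history, biopsy results, imaging studies and will be collected". Section 14.1 does not say how any of this bears on disease status.

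**The concern.** Sensitivity needs a denominator of men known to have the disease. In Arm 2 the denominator implied by section 2.3 is everyone who met the entry rule. For post-radiation men that rule is weak, because a nadir is the lowest value on record and a later value in a man with flat PSA will often lie above it.

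Two results are exposed. A non-recurrent man with a negative scan counts as a missed cancer and lowers apparent sensitivity in his PSA band. He also joins the PET-negative group in the Wilcoxon comparison. If his PSA is low, he helps to create a PSA difference that has nothing to do with detection. If it is close to that of the PET-positive men, he dilutes a real difference. Section 2.3 intends the PSA-band figures as the yardstick for comparison with the next agent, so their meaning matters beyond this pilot.

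**Working it through.** **1. The plan's own figure.** Inputs from section 14.1: log PSA means 0.06 and 0.98, SD 1.3, two-sided 5% Wilcoxon test. The difference is 0.92, and exp(0.92) = 2.51, the stated 2.5-fold ratio. Simulated power is 80.8% at 26/52 (stated 80%) and 46.5% at 12/23 (stated 48% for 35 men). The sample size reproduces; the issue is who is counted as a case.

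**2. How easily a stable man qualifies.** Take k exchangeable readings with no trend. The last exceeds the lowest earlier one unless it is itself the lowest, so P = 1 − 1/k = (k − 1)/k. This gives 67% for k = 3 and 83% for k = 6. With true PSA 0.2–0.5 ng/ml, an assumed CV of 5–15% and rounding to 0.01 (which creates ties), simulation gives 51–65% for k = 3 and 70–82% for k = 6.

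**3. Verification so far.** Biopsy or supportive clinical information exists for 7 + 4 = 11 men. That is 11/31 = 35% of those scanned.

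**4. Effect on the positivity rate (illustration).** Assume 65% detection in recurrent men (section 2.3 has 20/31 = 64.5% positive). Let 10% of the arm (0.10 × 78 = 7.8 men) be non-recurrent, with 10–20% positive scans.

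- 0.90 × 0.65 + 0.10 × 0.10 = 0.595
- 0.90 × 0.65 + 0.10 × 0.20 = 0.605

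A true 65% would read about 60%.

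**5. Effect on the Wilcoxon test (illustration).** Same mix, n = 78, with detection in recurrent men made independent of PSA (log PSA mean 0.66, SD 1.3). Log SD in non-recurrent men is assumed to be 0.6. Nominal rejection is 5%.

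| Median PSA of non-recurrent men (ng/ml) | Rejection rate |
|---|---|
| 0.5 | about 13–17% |
| 1.0 | about 6–8% |
| 2.0 | about 5% or less |

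The bias can also run the other way. Under the planned alternative, with 8 of the 26 PET-negative men non-recurrent, power is 96% if their geometric mean PSA is 0.5 and 62% if it is 2.0.

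**6. What a sustained-rise rule can do.** If the last two PSA steps must both rise, a stable man meets the rule 6–15% of the time (inputs as in step 2). If two consecutive rises anywhere in the record suffice, he meets it 22–47% of the time for k = 6 and 31–62% for k = 8, so the wording matters. The last-two rule has its own cost: with an assumed 12-month doubling time, three-monthly PSA and CV 10–15%, it misses about 23–42% of men whose PSA is truly rising.

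**The case against.** **Stable men may rarely be referred.** Arm 2 is described as biochemical relapse, and nothing shows that men with flat PSA enter it. A reader might infer from step 2 that half or more of the post-radiation men have no recurrence. The documents do not support that: the figure is the chance that a stable man would qualify, and the number of stable men presenting is unknown.

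**The documents hint at a limit on the mix.** Section 4.4 offers catheters to Arm 2 men who have had a prostatectomy, and section 2.3 reports over 20 of 31 men scanned with irrigation catheters. If section 4.4 was followed, men without prostatectomy are at most about 10/31 = 32%. For 10%, 15% or 20% of the arm to be non-recurrent, about 31%, 46% or 62% of them would have to be (0.10, 0.15 and 0.20, each divided by 10/31). This weakens the larger scenarios. It is not firm: section 4.4.1 words catheter use for all Arm 2 men, some prostatectomy patients may also have had radiation, and the 31 need not represent the final 78.

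**Wilcoxon inflation depends on an unsourced PSA level.** This stands. Step 5 shows that the inflation nearly disappears by a median of 1.0, and no section gives the PSA of non-recurrent men.

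**The denominator is inferred.** Section 14.1 names none, and the assumption that all men have recurrence is rationale text about preliminary results. That is fair, but section 2.3 gives sensitivity by PSA as the purpose of the expansion, and no other section supplies a reference standard.

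**Restricting the main analysis to confirmed men would add a bias.** Under section 4.8, suspicious uptake is reported to the referring physician, who may then biopsy. Confirmation therefore favours PET-positive men. This stands and shapes the fix.

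**Conclusion.** The point holds as a gap in definition and analysis. Entry and disease label rest on the same PSA rise, which for post-radiation men needs neither a minimum size nor a repeat value. Section 14.1 has no rule that uses follow-up to check or reclassify anyone. The PSA-band results can be read as positivity rates in men who met the entry rule, but not as sensitivity against established recurrence.

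The size is unknown. The documents give neither the post-radiation share of Arm 2 nor the PSA history behind each nadir. A drop from 65% to about 60% and a rejection rate of 13–17% belong to one assumed scenario: 10% non-recurrent, 10–20% positive scans and, for the test, median PSA 0.5. A reader might conclude that the Wilcoxon test is bound to find a false PSA effect. It is not: the direction and size depend on the PSA of the non-recurrent men. The 26/52 sample size is not in question.

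**What to change.** Amend section 14.1 (Amendment E Addendum) and leave entry unchanged.

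1. Keep all evaluable Arm 2 men as the main set. Report the PSA-band results as the PET-positivity (detection) rate in men meeting the entry rule, not as sensitivity against confirmed recurrence.
2. Prespecify a sensitivity analysis of both the PSA-band rates and the Wilcoxon comparison that sets apart post-radiation men without a sustained rise, and report those men separately. Define a sustained rise from PSA alone, up to the scan and blind to its result; for example, the last two consecutive PSA steps both rising. State how men with fewer than three pre-scan values are classed, since two steps need three values and entry guarantees only a nadir and a later one.
3. Tabulate biopsy or imaging confirmation during follow-up by PET result, but do not use it to select the main set, because work-up depends on the scan.

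The cost is SAP wording and extraction of PSA histories. The sensitivity set will be smaller than 78 and is likely to have fewer PET-negative men than the 26 planned, so it will have less power. A last-two-rises rule will also leave out some truly recurrent men (step 6). For that reason it belongs in a sensitivity analysis and not in the main one.

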3.2 Exclusion Criteria

- 3.2.1 Subjects for whom participating would significantly delay the scheduled standard of care therapy.
- 3.2.2 Subjects with any coexisting medical or psychiatric condition that is likely to interfere with study procedures and/or results.
- 3.2.3 Subjects with severe claustrophobia unresponsive to oral anxiolytics
- 3.2.4 Other medical conditions deemed by the principal investigator (or associates) to make the subject unsafe/ineligible for protocol procedures.
- 3.2.5 Subjects weighing > 350 lbs. (weight limit for scanner table), or unable to fit within the imaging gantry
- 3.2.6 Serum creatinine > 2 times the upper limit of normal
- 3.2.7 Total bilirubin > 2 times the upper limit of normal
- 3.2.8 Liver transaminases (ALT, AST) greater than 3 times the upper limit of normal

3.3 Screening Evaluation

Subjects will be seen by their treating NCI physician and be scheduled to undergo a multiparametric 3T MR in the NCI Molecular imaging center as standard of care for Arm 1. Confirmation of disease will be made following standard of care biopsy or prostatectomy (not part of this protocol) and slides must be reviewed by the Pathology staff at NIH. For presumed biochemical recurrence (Arm 2) or metastatic disease (Arm 3) conventional imaging studies and pathology confirmation of the diagnosis of adenocarcinoma of the prostate are required. Outside imaging studies can be used to include/exclude metastatic disease; however the images must be made available in DICOM format for review by MIP staff.

A screening visit will be performed within 21 days before administration of ¹⁸F DCFBC. Subjects will be permitted to continue taking any routine or necessary medication.

All subjects must satisfy all the inclusion criteria and none of the exclusion criteria listed in Section 3.1. Signed, dated and timed informed consent must be obtained from all subjects before any study-specific procedures are performed.

The following data will be collected:

- Date of birth
- Weight
- Height
- Prior and concurrent medications
- Medical history and concurrent diseases
- Results of screening tests: physical examination; vital signs; PSA test

CC Protocol Number: 14-C-0140
Abbreviated Title: DCFBC in prostate cancer
Version date: 10/27/2015
CIP #: 9622

Personal data (including contact information) will be collected with the subject's permission and only to the extent that is necessary for the purposes of the study. Blood samples for clinical laboratory tests will be drawn and include a CBC, Acute Care Panel, Hepatic Panel and PSA. Vital signs (BP, HR, RR and Temperature) will be recorded. Temperature will only be recorded at baseline, and following the completion of each PET/CT. A limited physical examination will be performed (if not performed within 30 days of ^{18}F DCFBC injection).

3.4 Inclusion of Women and Minorities

Members of all races and ethnic groups are eligible for this trial. Women are excluded from this trial as prostate cancer does not occur in females.

3.5 Registration Procedures

Authorized staff must register an eligible candidate with NCI Central Registration Office (CRO) within 24 hours of signing consent. A registration Eligibility Checklist from the web site (<http://home.ccr.cancer.gov/intra/eligibility/welcome.htm>) must be completed and faxed to [contact]. Verification of Registration will be forwarded electronically via e-mail to the research team. A recorder is available during non-working hours.

4 STUDY IMPLEMENTATION

4.1 Study Design

This is an open-label, 3-armed single-center pilot study. 110 evaluable subjects will be enrolled into the study (12 evaluable patients in arm 1; 78 evaluable patients in arm 2, and 20 evaluable patients in arm 3). An evaluable patient is defined as a patient who completes all required study procedures according to the assigned study arm. In order to allow for a small number of nonevaluable patients, the accrual ceiling will be set at 125.

Informed consent will be obtained prior to study enrollment. All subjects will undergo ^{18}F DCFBC injection and PET/CT imaging.

Patients in Arms 1 and 2 will undergo a single ^{18}F DCFBC PET/CT.

Patients in Arm 1 will have undergone a standard of care biopsy or clinically indicated prostatectomy. Specimens will be whole mounted on glass slides and regions of malignant tumor will be marked by the pathologist.

When possible, uptake of ^{18}F DCFBC depicted on PET/CT in Arms 2 and 3 will be validated with biopsy.

Patients in Arm 2 will be followed for clinical, imaging or pathologic data that may be obtained by their medical team within 12 months of imaging to determine if associations with ^{18}F DCFBC PET/CT can be seen.

CC Protocol Number: 14-C-0140
Abbreviated Title: DCFBC in prostate cancer
Version date: 10/27/2015
CIP #: 9622

Subjects in the metastatic disease arm (Arm 3) (as well as individuals who cross over into Arm 3) will undergo 2 separate ^{18}F DCFBC PET/CT imaging sessions, one at initial enrollment, and a second upon clinical follow-up (4-6 months after baseline ^{18}F DCFBC).

Patients in Arm 3 will also undergo a whole body Na^{18}F PET/CT scan within 3 weeks of each ^{18}F DCFBC to assess for potential early bone metastases. Changes in distribution of each radiotracer over the 4-6 month period will be compared with clinical data and imaging (obtained as standard of care) at that time. Each ^{18}F DCFBC PET/CT will be compared with the corresponding Na^{18}F PET/CT scan when obtained.

4.2 Stratification Procedures

4.2.1 Categories

- ARM 1
 - For patients in the localized disease arm, a multiparametric MRI (standard of care at the NIH Clinical Center) with findings suggestive for prostate cancer must be performed in the NCI Molecular Imaging Clinic (MIC) within 4 months of enrollment and histopathologic confirmation of prostate cancer must be done
- ARM 2
 - Patients enrolling into the biochemical relapse arm:
 - For patients status post radiation therapy, any PSA increase from post radiation therapy nadir
 - OR**
 - For patients status post prostatectomy, a PSA ≥ 0.2 ng/ml
 - Nonspecific or no evidence for disease on standard imaging modality
- ARM 3
 - Patients in the metastatic monitoring arm must have identifiable metastatic disease on at least 1 imaging modality.

4.3 Drug Administration

4.3.1 ^{18}F DCFBC

See Section [7.1.5](#).

4.3.2 ^{18}F NaF Injection

See section [7.2.4](#)

4.4 ^{18}F DCFBC PET/CT Imaging

All images will have personal subject identification removed and will be assigned unique subject identification.

Patients will be instructed to maintain good hydration for the 24 hours prior to the ^{18}F DCFBC PET/CT (recommended 1-2 liters of fluid, unless medically contraindicated).

CC Protocol Number: 14-C-0140
Abbreviated Title: DCFBC in prostate cancer
Version date: 10/27/2015
CIP #: 9622

Patients will report to the NCI Molecular Imaging Clinic (MIC) on the day of their ^{18}F DCFBC PET/CT imaging sessions and peripheral venous access will be obtained. The patient will be encouraged to void prior to positioning in the PET/CT scanner.

Patency of the venous access will be demonstrated with a saline flush and the patient will then receive 8 mCi of ^{18}F DCFBC as an IV bolus.

Dynamic PET/CT imaging of a single bed position (including the prostate bed) will be performed for 45-min for patients in Arm 1 and 2 then, at 60 minutes post injection of ^{18}F DCFBC. A static whole body PET/CT will be performed then repeated again at 2hrs post injection. Only a single injection of ^{18}F DCFBC is required. The initial 45 minutes dynamic regional scan will be used to determine the kinetics of ^{18}F DCFBC in the tumor as compared with normal prostate and other background.

Patients in Arm 3 will only have static whole body PET/CTs performed at 60 minutes post injection and again at 2 hrs post injection. As previous studies have suggested, increased T:B uptake is seen at 2 hours compared with 1 hour after radiotracer injection. After 5 patients are imaged in each arm, an interim analysis will be done to determine the utility of imaging at 2 hrs.

Patients in Arm 2 who have had a prostatectomy may have a 2 or 3 lumen urinary catheter inserted to improve visualization of the bladder and adjacent anatomy during imaging. The urinary catheter is inserted prior to injection and is removed once all scans are completed. The 3 lumen catheter will be used to irrigate and empty the bladder during the scan. One lumen is used to inflate the balloon to secure the catheter in the bladder, the second lumen allows for continuous drainage of urine from the bladder during imaging and the third lumen allows for inflow of fluids. The catheter will be attached to an irrigation system that will allow for better visualization of the bladder and adjacent anatomy.

After the patient is injected with the radiotracer, the bladder will be filled with up to 500cc of saline via the third inflow arm of the urinary catheter. The outflow arm is attached to the drainage bag which has a clamp. The clamp on the drainage bag will be closed to allow for collection of the urine in the bladder. Approximately ten minutes before the patient is scanned the clamp on the drainage bag will be opened to allow for drainage of the bladder. The clamp will remain open during the imaging session to allow for continuous drainage of the bladder. This procedure will be repeated prior to the 2 hrs post-injection scan. Once all scans are completed the catheter will be removed.

A 2 lumen catheter will be used in lieu of the 3 lumen catheter to keep the bladder empty, if the patient cannot tolerate the insertion of a 3 lumen catheter.

If a patient is not able to tolerate catheter placement, they will be asked to empty their bladder frequently during the PET uptake phase and immediately prior to whole body PET/CT imaging.

CC Protocol Number: 14-C-0140
Abbreviated Title: DCFBC in prostate cancer
Version date: 10/27/2015
CIP #: 9622

A corresponding low dose CT scan for attenuation correction and co-registration purposes will be performed prior to each PET image (i.e. 1-single bed position including the prostate bed, and 2 whole body (1 each for the 1-hr and 2 hr images). All whole body ^{18}F DCFBC PET/CT images will be obtained from the top of the skull down to the thighs.

4.4.1 Summary of scanning procedure:

1. IV placement
2. If not previously drawn within 30 days of ^{18}F DCFBC, blood will be drawn for PSA measurement
3. Subject asked to void (Arm 2 patients will receive a urinary catheter which will be removed once all imaging is completed).
4. Administration of ^{18}F DCFBC; begin AE monitoring
5. Initial positioning in the scanner and single bed position low dose transmission CT
6. For Arm 1 and Arm 2 patients: 45-minute dynamic imaging of the pelvis
7. Subject asked to void
8. 1 hour following ^{18}F DCFBC injection, whole body PET/CT imaging will be performed (~45 minutes in duration)
9. Another whole body PET/CT scan will be performed (~45 minutes) at 2 hours post-injection of ^{18}F DCFBC
10. Follow-up AE query ~1-3 days post-injection

4.5 ^{18}F NaF PET/CT Imaging

^{18}F NaF PET/CT Imaging (only in ARM 3 subjects, may be performed as clinical standard of care in this or other arms)

Patients undergoing ^{18}F NaF PET/CT Imaging at NCI/MIC are instructed to maintain good hydration for the 24 hours prior to the ^{18}F NaF PET/CT (recommended 1-2 liters of fluid, unless medically contraindicated). Patients will report to the NCI MIC on the day of their ^{18}F NaF PET/CT imaging sessions and peripheral venous access will be obtained (most commonly via IV in the antecubital fossa). The patient will be encouraged to void prior to positioning in the PET/CT scanner. A low dose non-diagnostic transmission CT will be performed. Patency of the venous access will be demonstrated with a saline flush and the patient will then receive 3mCi of ^{18}F NaF IV bolus.

